## **1 Introduction**

This document is a clinical trial protocol. This research will be conducted based on the standards of the Good Clinical Trial Method and regulations from the relevant institutions and ethics committees.

### ***1.1 Background***

Acne vulgaris (AV) is a chronic inflammatory disease with multifactorial causes in the skin's pilosebaceous follicular units, with clinical manifestations in the form of comedones, papules, pustules, nodes, and pseudocysts. The following factors are considered important for the etiology of AV: increased rate of sebum excretion, endocrinological factors such as androgens, abnormal keratinization of the follicular infundibulum, the proliferation of *Cutibacterium acnes* (*C. acnes*), and inflammation. Recent studies at the molecular and cellular levels have clarified how these factors interact and the role of the innate immune system. Inflammatory processes have been demonstrated in all types of lesions – preclinical microcomedones, comedones, inflammatory lesions, 'post inflammatory' erythema or hyperpigmentation, and scarring. Inflammation localized to the pilosebaceous can be considered a hallmark of acne and should be managed through several therapeutic routes. Clinicians tend to think that oral antibiotics should be used to treat inflammation in acne. However, this treatment are associated with resistance and low outcome due to its adverse events such as erythema, desquamation, and dry skin. There is evidence of the use and opportunity of vitamin D as a novelty treatment influencing the immune system. 25OHD and 1,25(OH)2D are both catabolized by CYP24A1. 1,25(OH)2D is a ligand for the vitamin D receptor (VDR), a transcription factor that binds to sites in DNA called vitamin D response elements (VDRE). Thousands of these binding sites regulate hundreds of genes through several signaling pathways in different cell types, including their regulation in immune cells by toll-like receptors (TLRs), the primary signaling nucleus of *C. acnes* that interacts with the innate immune system, causing acute and chronic inflammation.

## **2 Study Objectives**

### ***2.1 Primary Objective***

The primary objective of this study is to evaluate the efficacy and safety of combination topical vitamin D and supplementation as adjuvant therapy in acne vulgaris compared to placebo and topical vitamin D monotherapy.

### ***2.2 Secondary Objective(s)***

1. To assess vitamin D Receptor (VDR) expression on acne lesion and blood sample
2. To assess the effect of combination topical vitamin D and supplementation on IL-1 $\beta$  expression on acne lesion
3. To assess the effect of combination topical vitamin D and supplementation on IL-6 expression on acne lesion
4. To assess the effect of combination topical vitamin D and supplementation on IL-10 expression on acne lesion
5. To assess the effect of combination topical vitamin D and supplementation on IL-17 expression on acne lesion

## **3 Study Design**

### ***3.1 General Design***

It is a randomized double-blinded controlled trial to assess the efficacy and safety of combination topical vitamin D and supplementation as adjuvant therapy in acne vulgaris compared to placebo and topical vitamin D monotherapy. In week 8th, the patients will be observed to see if there is any recurrence of the lesion.

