### ***3.3 Primary Study Endpoints***

- Clinical symptoms  
Changes in counts of inflammation and non-inflammation lesions (assessed in week 8th)
- Changes in VDR, IL-1 $\beta$ , IL-6, IL-10 and IL-17 expression on acne lesion (Time frame: change of expression from baseline to week 8th)

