#### ***4.3 Early Withdrawal of Subjects***

The protocol treatment will be discontinued if patients

- a. There are severe side effects in the subject in the form of gastrointestinal disorders, severe liver function disorders, and severe irritation, edema or bullous lesions at the site of topical drug application.
- b. Subjects decided to withdraw from the study before the second week.
- c. Subjects did not come for 2 consecutive follow-ups. The tolerance limit for follow-up is D+3 from the specified examination date.
- d. Subject confirmed positive for COVID-19
- e. Subjects did not follow established research protocols.

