## 5. Study Procedures

### *Treatment phase:*

The selected subjects were divided into three groups through a process of randomization and sample stratification per group. The first group (A) will receive a combination of oral vitamin D 2000 IU 1x1 and topical 7-Dehydrocholesterol 5000 mcg 2x1, the second group (B) will receive an oral placebo and topical 7-Dehydrocholesterol 5000 mcg 2x1 and the third group (C) will receive an oral placebo and basic ingredient placebo topical vitamin D similar to the ointment to be tested. All subjects were still given 0.1% adapalene cream as a standard topical treatment for AV. The three groups will receive intervention for 8 weeks (56 days). AV lesion extraction will be performed, peripheral venous blood sampling will be performed to examine serum 25(OH)D and serum VDR. Examination of serum VDR and tissue VDR were using flowcytometry. Examination of inflammatory cytokines IL-1 $\beta$ , IL-6, IL-10, and IL-17 in tissues were using the Luminex Kit. Random allocation is done by block randomization technique using a computer program (Randlist®). Capsule drugs will be recalculated and topical drugs will be weighed when the subject returns for follow-up. Research drugs when given to subjects or returned to researchers were included in sealed envelopes. Each subject received a diary sheet which included a statement column to drink/not drink/apply/not apply and have/no side effects and their type, which had to be filled in every day according to the diary attached.

*Arms and intervention*

Arm	Intervention/treatment
Experimental: combination topical vitamin D and supplementation Daily supplementation (1x/day, in the morning) and topical application (2x/day, in the morning and in the afternoon, minimum duration 4 hours on the skin) for 56 days	Drug: combination vitamin D 2000 IU 1x1 and topical 7-Dehydrocholesterol 5000 mcg 2x1
Active Comparator: oral placebo and topical vitamin D Daily supplementation (1x/day, in the morning) and topical application (2x/day, in the morning and in the afternoon, minimum duration 4 hours on the skin) for 56 days	Drug: oral placebo and topical 7-Dehydrocholesterol 5000 mcg 2x1
Placebo Comparator: Daily supplementation (1x/day, in the morning) and topical application (2x/day, in the morning and in the afternoon, minimum duration 4 hours on the skin) for 56 days	Drug: oral placebo and basic ingredient placebo topical vitamin D similar to the ointment

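### Does checking for recurrence in week 8, the week treatment ends, leave the trial with a result it cannot deliver?

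*Protocol*

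**What the plan says.** Three parts of the protocol bear on this.

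- **Section 3.1 (General Design)** names one time point, week 8, and says that then "the patients will be observed to see if there is any recurrence of the lesion". It does not define recurrence or say from what state a lesion would have to return.
- **Section 5 (Study Procedures, treatment phase)** fixes the duration: "The three groups will receive intervention for 8 weeks (56 days)". The arms table repeats 56 days for each arm. Background therapy is common to all: "All subjects were still given 0.1% adapalene cream as a standard topical treatment for AV".
- **Section 3.3 (Primary Study Endpoints)** sets the clinical endpoint as "Changes in counts of inflammation and non-inflammation lesions (assessed in week" 8), and the expression endpoints as "change of expression from baseline to week 8 th".

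No washout and no visit after week 8 is described. The only slack in timing is in section 4.3: "The tolerance limit for follow-up is D+3 from the specified examination date".

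**The concern.** In dermatology, recurrence usually suggests that lesions return after treatment has stopped. To see that, patients must be watched for some time off treatment. Here the end of treatment, the primary reading and the recurrence check all fall in week 8, with every arm treated up to that point. A lesion present then might be new, might have returned, or might never have cleared.

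If a recurrence result were reported from this visit as relapse after treatment, it would largely restate the week-8 lesion count under another name. A statement that the combination prevents relapse would have no support in the design. Because section 3.1 presents the check as a feature of the trial, the mismatch with sections 3.3 and 5 deserves a look.

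**Working it through.** **1. The protocol's own duration.** Section 5 gives it in weeks and in days: 8 × 7 = 56. The two agree.

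**2. Time off treatment before the check.**
- End of treatment (section 5): day 56.
- Recurrence check (section 3.1) and primary reading (section 3.3): week 8, taken as day 56.
- Planned time off treatment: 56 − 56 = 0 days.
- With the full tolerance of section 4.3: (56 + 3) − 56 = 3 days. This is an allowance for late attendance, not a follow-up period.

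So recurrence after treatment is not observable, and the premise of the concern is confirmed.

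**3. What depends on recurrence.** The word can be looked for in each place where a planned result is fixed.

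| Section | Content | Recurrence used? |
|---|---|---|
| 2.1 | Primary objective: efficacy and safety | No |
| 2.2 | Secondary objectives: VDR and four interleukins | No |
| 3.3 | Primary endpoints: lesion counts, expression changes | No |
| 3.4 | Safety endpoints: adverse events | No |
| 4.4 | Sample size: proportions improved, 0.95 against 0.70 | No |
| 6.1 | Target sample size | No |

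The sample size stands without it: 28 per group from section 4.4, 28 / (1 − 0.2) = 35 after allowing for drop-out, and 3 × 35 = 105.

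**4. The two readings of the sentence.**
- *Return after treatment stops.* This cannot be observed, by step 2. The visit then serves only as the end-of-treatment assessment that section 3.3 already describes.
- *Reappearance during treatment.* This is not excluded by the schedule. Section 4.3 withdraws patients who miss two follow-ups in a row, so at least two are scheduled. If week 8 is the last of them, at least one comes earlier. Section 5 also has drug returns counted and weighed at follow-up. The protocol does not say whether lesions are examined at those visits, so earlier lesion status may or may not be known. Under this reading the gap is a missing definition.

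**5. Effect of an edit.** Suppose the sentence were deleted, or replaced by a description of week 8 as the end-of-treatment assessment. The visit would still take place in week 8, the same counts and expression changes would be measured, and the sample size and the conclusions sought under sections 2.1 and 2.2 would be the same.

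**The case for a change.** The strongest argument for a change is that an undefined outcome outside the endpoint list invites reporting after the fact. A statistical analysis plan could define how recurrence is analysed, but it could not create observation time that the protocol does not schedule. And whichever meaning was intended, the sentence is imperfect: either it names something the schedule cannot show, or it omits a definition. Correcting it would cost one sentence.

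Part of this stands. The timeline is right, and any claim about relapse after treatment would be unsupported. The tension between section 3.1 and sections 3.3 and 5 is real.

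The rest does not carry the point. No recurrence rate, comparison or claim is planned anywhere, so the unsupported claim is hypothetical. Counting the efficacy endpoint twice would need a second endpoint, and none is listed. To say that a lesion seen in week 8 could never be told apart from non-response goes further than the text allows, because there is at least one follow-up before week 8 at which lesion status might be recorded. The low cost of an edit is no reason for one if nothing measured, analysed or concluded would differ.

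**Conclusion.** The observation is correct, but no change to the plan is needed. Planned time off treatment at the recurrence check is 0 days (at most 3 with visit tolerance), so the trial cannot speak to relapse after treatment. It does not set out to do so: recurrence enters none of the objectives, endpoints, safety measures or sample-size inputs. An analyst working from section 3.3 would treat week 8 as the end-of-treatment assessment and lose nothing.

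This rests on three assumptions: that the week-8 visit falls at day 56 within the stated tolerance, that no post-treatment visit exists beyond those described, and that recurrence is not made a formal outcome in a document not shown here. If the last failed and post-treatment recurrence were analysed as an outcome, the point would become substantive, because the schedule could not supply the data. On the protocol as it stands, the effect on the planned estimates and tests is nil.

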### ***3.2 Settings and Conduct***

This study was performed in Central Jakarta, Jakarta Capital Special Region, Indonesia. Patients were assigned into three groups. The first group was given the combination of topical vitamin D and supplementation also standard treatment with topical adapalene. In

comparison, the second group was given topical vitamin D monotherapy and standard treatment with topical adapalene. Last group was given only the standard treatment with topical adapalene as control group.

### ***3.3 Primary Study Endpoints***

- Clinical symptoms  
Changes in counts of inflammation and non-inflammation lesions (assessed in week 8th)
- Changes in VDR, IL-1 $\beta$ , IL-6, IL-10 and IL-17 expression on acne lesion (Time frame: change of expression from baseline to week 8th)

### ***3.4 Primary Safety Endpoints***

Adverse events will be assessed during study periods. Any adverse events including local/skin inflammation caused by either oral or topical vitamin D will also be monitored by dermatologist in charge.

## **4 Subject Selection and Withdrawal**

### ***4.1 Inclusion Criteria***

- a. Men and women diagnosed with moderate or severe acne vulgaris
- b. Aged over 18-50 years.
- c. During the study, were willing not to use skin care products either in oral and/or topical form on the face, as well as other treatments outside of standard AV treatment.
- d. Willing to take part in the examination and treatment in accordance with the provisions of the study and follow the control time schedule in accordance with the predetermined research plan also willing to sign the informed consent form.

### ***4.2 Exclusion Criteria***

Patients will be excluded if

- a. Women who are pregnant and breastfeeding.
- b. Have history using topical antibiotics in the past 2 weeks.

- c. Have history using topical corticosteroids in the past 2 weeks.
- d. Have history taking vitamin D supplements in the last 1 month.
- e. Have history taking oral antibiotics in the last 1 month.
- f. Have history using oral corticosteroid use in the last 1 month.
- g. Have history using oral and topical retinoid use in the last 3 months.
- h. Have history using topical BPO in the last 1 month.
- i. Using hormonal contraception for women.
- j. Have history of drug allergies or skin disorders due to side effects of first-line therapy drugs for moderate/severe acne vulgaris.
- k. Impaired liver and kidney function.

#### ***4.3 Early Withdrawal of Subjects***

The protocol treatment will be discontinued if patients

- a. There are severe side effects in the subject in the form of gastrointestinal disorders, severe liver function disorders, and severe irritation, edema or bullous lesions at the site of topical drug application.
- b. Subjects decided to withdraw from the study before the second week.
- c. Subjects did not come for 2 consecutive follow-ups. The tolerance limit for follow-up is D+3 from the specified examination date.
- d. Subject confirmed positive for COVID-19
- e. Subjects did not follow established research protocols.

#### ***4.4 Sample Estimate***

The sample size in this study can be calculated based on the ratio of two proportions, using the following formula:

$$N1 = N2 = \frac{(Z\alpha\sqrt{2PQ} + Z\beta\sqrt{P_1 Q_1 + P_2 Q_2})^2}{(P_1 - P_2)^2}$$

N1 = Control group sample size

$N_2 = N_3 =$  The number of samples of the test group

$\alpha =$  Type 1 error, set at 0.10 (90% confidence level) with a one-way hypothesis, so

$$Z \alpha = 1,64$$

$\beta =$  if it is set at 20%, then the power of this study is  $1 - \beta = 80\%$ , from the table so that  $Z \beta = 0.84$

$P_2 =$  The proportion of treatment effectiveness in the control group obtained from the previous research was  $P_2 = 0.70$

$$Q_2 = 1 - P_2 = 1 - 0,70 = 0,30$$

$P_1 - P_2 =$  The minimum difference in the proportion of treatment effectiveness that is considered significant is set at 0.25.

$$P_1 = P_2 + 0,20 = 0,70 + 0,25 = 0,95$$

$$Q_1 = 1 - P_1 = 1 - 0,95 = 0,05$$

$$P = \frac{P_1 + P_2}{2} = 0,825$$

$$Q = 1 - P = 1 - 0,825 = 0,175$$

Obtained results:

$$\begin{aligned} N_1 = N_2 &= \frac{(1,64\sqrt{2 \times 0,825 \times 0,175} + 0,84\sqrt{0,95 \times 0,05 + 0,70 \times 0,30})^2}{(0,25)^2} \\ &= 27,35 \\ &= 28 \end{aligned}$$

Assuming that the difference in the proportion of moderate/severe acne vulgaris improvement between the group with standard therapy + oral vitamin D and topical vitamin D and the control group was only 25%, so the sample size for each group was 28 people.

Anticipation of drop out by 20%:

$$n' = \frac{n}{(1-f)}$$

$$n' = \frac{28}{(1-0,2)} = 35 \approx n_1 = n_2 = n_3 = 35 \text{ people.}$$

Information:

$n'1 = n'2 = n'3$	= the size of the research sample for each group
$n'$	= sample size after correction with anticipation of DO
$n$	= sample size based on previous estimates
$f$	= prediction of the percentage of sample drop out

The sample size after being corrected with anticipation of dropping out became  $n'1 = n'2 = n'3 = 35$  people.

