**6 Sample Size**

**6.1 Target sample size**

105 patients (35/arm)

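### The sample size section derives Zα = 1.64 from a one-sided type 1 error of 0.10, but one-sided 0.10 gives 1.28

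*Protocol*

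**What the plan says.** Section 4.4 (Sample Estimate) uses a normal-approximation formula for two proportions. It describes α as "Type 1 error, set at 0.10 (90% confidence level) with a one-way hypothesis, so", with Zα = 1.64 given as the consequence. The same 1.64 is then entered in the worked formula.

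The other inputs are:

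- **Power:** for β, "if it is set at 20%, then the power of this study is" 80%, with Zβ = 0.84.
- **Control proportion:** "The proportion of treatment effectiveness in the control group obtained from the previous research was" 0.70.
- **Difference:** "The minimum difference in the proportion of treatment effectiveness that is considered significant is set at 0.25", so the test proportion is 0.95.

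The result is 27.35, "so the sample size for each group was 28 people". A 20% allowance for dropout brings this to 35 per group, and Section 6.1 gives the total as 105. No other part of the protocol states an alpha or says whether tests are one- or two-sided.

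**The concern.** The protocol presents 1.64 as what follows from a one-sided error of 0.10. It does not follow, so at least one of the three items (the alpha, the sidedness, the Zα) is mis-stated.

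Two things are at stake. First, this is the only error level in the protocol and an input to its sample size, yet anyone who starts from the level as worded arrives at a different number of patients. Second, if the analysis takes its test level from this line, the two readings differ by a factor of two in one-sided error (0.10 against 0.05). A one-sided p-value between those limits would then count as significant on one reading and not on the other. The second point is conditional: the protocol does not say that the test level comes from here, and the SAP is not at hand.

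**Working it through.** **Inputs, all from Section 4.4:** P1 = 0.95, P2 = 0.70, P = 0.825, Q = 0.175, d = 0.25, Zβ = 0.84, dropout f = 0.20. There are three equal arms.

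**Formula:** n = (Zα√(2PQ) + Zβ√(P1Q1 + P2Q2))² / d²

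- √(2PQ) = √(2 × 0.825 × 0.175) = √0.28875 = 0.5374
- √(P1Q1 + P2Q2) = √(0.0475 + 0.21) = √0.2575 = 0.5074
- d² = 0.0625

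**Step 1: reproduce the protocol's figure with Zα = 1.64.**
n = (1.64 × 0.5374 + 0.84 × 0.5074)² / 0.0625 = (0.8813 + 0.4263)² / 0.0625 = 27.35, so 28. Then 28 / 0.8 = 35 per arm, and 3 × 35 = 105. This matches Sections 4.4 and 6.1.

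**Step 2: which alpha belongs to which Z.**

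| Z | One-tail area | Two-tail area |
|---|---|---|
| 1.28 | 0.1003 | – |
| 1.64 | 0.0505 | 0.1010 |

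The exact quantile for one-sided 0.10 is 1.2816. For one-sided 0.05, and equally for two-sided 0.10, it is 1.6449.

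**Step 3: sample size under each reading, same formula.**

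| Reading | Zα | n | Evaluable per arm | Enrolled per arm | Total |
|---|---|---|---|---|---|
| One-sided 0.10, as worded | 1.28 | 19.86 | 20 | 25 | 75 |
| As calculated | 1.64 | 27.35 | 28 | 35 | 105 |
| One-sided 0.05 or two-sided 0.10 | 1.645 | 27.47 | 28 | 35 | 105 |

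Using 1.2816 instead of 1.28 gives 19.89, still 20.

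**Step 4: power at 28 per group.**
Power = Φ((d√n − Zα√(2PQ)) / √(P1Q1 + P2Q2)), with d√28 = 1.3229.

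- Zα = 1.2816: Φ((1.3229 − 0.6887) / 0.5074) = Φ(1.25) = 0.894
- Zα = 1.64: Φ((1.3229 − 0.8813) / 0.5074) = Φ(0.87) = 0.808
- Zα = 1.645: 0.806

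By the same formula, the difference from 0.70 detectable with 80% power at 28 per group is 0.219 at one-sided 0.10 and 0.248 at Zα = 1.64.

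**Step 5: exact power as a cross-check**, enumerating all outcomes of two binomials with n = 28 and proportions 0.95 and 0.70.

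| One-sided level | Pooled z test | Fisher's exact test |
|---|---|---|
| 0.10 | 0.919 | 0.848 |
| 0.05 | 0.851 | 0.702 |

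At one-sided 0.10, power exceeds 80% by the normal approximation and by both exact calculations. The 70% for Fisher's test at 0.05 reflects that test's conservatism. It is not caused by the mismatch discussed here.

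**The case against.** The strongest reply is that nothing of substance changes. The sample size follows exactly from the Zα printed. Two of the three possible corrections (two-sided 0.10 and one-sided 0.05) have the same critical value, the same sample size and the same error in the favourable direction. Under the third, 28 per group exceeds the 20 required. The mention of 90% confidence also suggests that two-sided 0.10 was meant. All of this is fair, and it is why the point is a correction to the text and not a challenge to the sample size. It does not remove the contradiction: the text explicitly says the hypothesis is one-sided, and one-sided 0.05 fits 1.64 just as well.

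A second reply is that power statements should not be stretched to the whole trial. That stands. Section 4.4 covers only the proportion improved, combination against control. Section 3.3 lists changes in lesion counts and marker expression as primary endpoints, and no difference is assumed against topical monotherapy. The power figures here apply to the Section 4.4 comparison only.

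Two other explanations can be excluded. The value is not a text-extraction error, because 1.64 appears both in the definition and in the worked formula. A continuity correction at one-sided 0.10 would also give 28, but this is coincidence: the printed formula has no such correction and uses 1.64 explicitly.

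Finally, the SAP may define the test level. It could, but that would not make this line of the protocol correct.

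**Conclusion.** The concern holds. An alpha of 0.10, a one-sided hypothesis and Zα = 1.64 are mutually inconsistent, and nothing else in the protocol shows which is wrong. Taken as worded, the level implies 75 patients against the 105 planned. Taken from the Zα used, it implies 105.

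The slip is conservative. For the Section 4.4 comparison of 0.95 with 0.70, 28 per group is enough at the alpha as worded (about 89% power) and also at the level that 1.64 represents (about 81%), both by the protocol's formula. Any consequence for the analysis depends on whether the test level is taken from this section, which cannot be seen from the protocol.

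**What to change.** In Section 4.4, state the level that was originally intended and make alpha, sidedness and Zα agree. One of the following would do:

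- *Two-sided 0.10 (90% confidence level), Zα = 1.645*, or *one-sided 0.05, Zα = 1.645*. Either keeps 28 evaluable and 35 enrolled per arm, with power about 81% by the protocol's formula.
- *One-sided 0.10, Zα = 1.28*, if that was truly meant. Keep the sample size and restate power as about 89%. Name the normal-approximation formula as the method, because exact power ranges from 85% to 92% with the test chosen.

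Use the same level in the analysis. The sponsor should report what was intended at planning, not choose a level now.

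While the section is open, correct the clerical 0.20 in the line for P1 to 0.25. The same line already continues with 0.25, so the sample size is unaffected.

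The cost is wording in one section, with no change to sample size, arms or procedures.

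### The 80% power in Protocol 4.4 belongs to an undefined response proportion that 3.3 does not list, so it is not established for any listed primary endpoint

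*Protocol*

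**What the plan says.** Protocol 4.4 uses a two-proportion formula with a control value of 0.70, taken from earlier research, and a target of 0.95: "The minimum difference in the proportion of treatment effectiveness that is considered significant is set at 0.25". The outcome is first called effectiveness of treatment. At the end of the calculation it becomes improvement, and the pair compared is combination against control: "Assuming that the difference in the proportion of moderate/severe acne vulgaris improvement between the group with standard therapy" and so on. The error rate is given as "Type 1 error, set at 0.10 (90% confidence level) with a one-way hypothesis", with Z alpha 1.64, and power is 80%. The result is 28 per group, 35 after allowing for 20% dropout, and 105 in total (section 6.1).

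Section 3.3 lists the primary endpoints. The clinical one is "Changes in counts of inflammation and non-inflammation lesions" at week 8. The other is change in VDR, IL-1β, IL-6, IL-10 and IL-17 "expression on acne lesion (Time frame: change of expression from baseline to week 8". Section 2.2 places the same markers under secondary objectives, for example "To assess vitamin D Receptor (VDR) expression on acne lesion and blood sample" and "To assess the effect of combination topical vitamin D and supplementation on IL-6 expression on acne lesion".

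**The concern.** The protocol fixes both the basis of its sample size and its list of primary endpoints, and the two do not correspond. The sizing outcome is binary; every listed primary endpoint is a change in a count or in an expression level. No cut-off, scale or time point says when a patient counts as improved, so the 0.70 cannot be matched to anything this trial is said to measure.

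A reader will take 80% as the chance of detecting the primary effect. For a mean change, power depends on a difference and an SD, and the protocol gives neither. The reader cannot tell what lesion-count difference 105 patients were meant to detect, and a null result on lesion counts would be hard to interpret. The differing rank of the markers in 2.2 and 3.3 also leaves it unclear which endpoints need a power statement at all.

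**Working it through.** **1. The plan's own figure.** Inputs from 4.4: P1 = 0.95, P2 = 0.70, P = 0.825, Q = 0.175, Z alpha = 1.64, Z beta = 0.84.

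- √(2 × 0.825 × 0.175) = 0.5374; times 1.64 = 0.8813
- √(0.95 × 0.05 + 0.70 × 0.30) = √0.2575 = 0.5074; times 0.84 = 0.4263
- (0.8813 + 0.4263)² / 0.25² = 27.35, rounded up to 28
- 28 / 0.8 = 35; 3 × 35 = 105

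The figure reproduces, for this proportion only.

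**2. Alpha against Z.** Z = 1.64 is one-sided 0.05 or two-sided 0.10. One-sided 0.10, as the text reads, is Z = 1.2816. The same formula then gives 19.89, that is 20 per arm.

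**3. What 28 per arm can detect for a mean change.** Assumptions: two-sample t-test on the mean change, 28 evaluable per arm (54 degrees of freedom), one pair of arms, one endpoint, no multiplicity adjustment. The noncentral t distribution with noncentrality d√(28/2), where d is the difference in SD units, gives:

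| | Z = 1.64 (one-sided 0.05 or two-sided 0.10) | Z = 1.28 (one-sided 0.10) |
|---|---|---|
| d for 80% power | 0.67 (0.673) | 0.57 (0.572) |
| Power at d = 0.5 | 58% | 72% |
| Power at d = 0.673 | 80% | 89% |
| Power at d = 0.8 | 91% | 95% |

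The normal approximation agrees closely: (1.645 + 0.842) × √(2/28) = 0.66. The values 0.5 and 0.8 are illustrations; the protocol states no standardised difference.

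**4. In lesions.** The protocol gives no SD. At an assumed SD of 5, 10 or 15 lesions, 0.673 SD is 3.4, 6.7 or 10.1 lesions.

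**5. If improvement were a threshold on lesion-count change.** Assume a normal change with equal variances and one common cut-off. Then 0.95 against 0.70 implies a shift of z(0.95) − z(0.70) = 1.645 − 0.524 = 1.12 SD. With 28 per arm, a t-test on means has about 99% power at Z = 1.64.

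**The case against.** The strongest reply is that improvement in moderate or severe acne is naturally read as a clinical responder outcome, probably a cut-off on lesion-count change, and that 3.3 puts lesion counts under clinical symptoms. On that reading the proportion is not foreign to the primary endpoint. Step 5 shows that the planning values would then imply ample power for a mean comparison. The cut-off might also stand in a statistical analysis plan that is not at hand.

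Much of this stands. It rules out a stronger conclusion that a reader might draw, namely that the trial is underpowered for lesion counts. The documents do not support that: power may lie above or below 80%, and the 0.5 to 0.8 SD range does not come from the protocol. Equally, the 99% rests on a threshold model that the protocol does not state, and it says nothing about VDR or the cytokines.

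The reply does not remove the mismatch. An analysis plan could supply the cut-off, but 3.3 would still list no proportion while 4.4 is sized on one.

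Two further limits are fair. A detectable difference worked back from a fixed N describes what that N can do; it does not justify it. And 3.2 is written in the past tense: if recruitment is over, a restated power helps interpretation but cannot alter the trial.

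**Conclusion.** The point holds in a limited form and should be fixed. The only power figure in the protocol applies to a response proportion without a stated cut-off, for combination versus control, and that proportion is not a listed primary endpoint. The 80% is therefore not established for any endpoint in 3.3. Nor does it cover combination versus topical monotherapy, although 2.1 names that comparison in the primary objective.

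The size of the gap cannot be fixed from the document. For each lesion-count change, 28 evaluable per arm give 80% power at 0.67 SD (Z = 1.64) or 0.57 SD (Z = 1.28), under a t-test on means for one pair and one endpoint without adjustment.

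Two inconsistencies bear directly on any restated figure. The stated one-way 0.10 does not match Z = 1.64. The markers on acne lesions are secondary in 2.2 and primary in 3.3; the blood VDR measurement in 2.2 does not appear in 3.3, so it is not part of that conflict.

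**What to change.** Keep 35 per arm and choose one of two routes.

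**(a) Restate the power.** Say in 4.4 that the 80% applies to the responder proportion for combination versus control. Then add, for example: with 28 evaluable per arm, combination versus control has 80% power at Z = 1.64 to detect 0.67 SD in the change to week 8 in the inflammatory lesion count, and separately in the non-inflammatory count (t-test on means, per endpoint, no multiplicity adjustment); with an SD of [value and source] this is [x] lesions; no power is claimed for combination versus topical monotherapy or for VDR and the cytokines. The sponsor should say why that lesion difference is worth detecting.

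**(b) Align the endpoint.** Define the week-8 responder cut-off so that it matches the source of the 0.70, and list that proportion in 3.3 as the primary endpoint.

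In either case, make alpha and sidedness agree with Z. If one-sided 0.10 is meant, Z is 1.28, the 4.4 formula gives 20 per arm, and 28 per arm detect 0.57 SD. Also give VDR and the four cytokines on acne lesions the same rank in 2.2 and 3.3.

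**Cost.** Route (a) needs wording and one sourced SD per lesion count, and the power statement may look less favourable. If the sponsor finds 0.67 SD too large, N must be reopened: 0.5 SD at Z = 1.64 needs 51 evaluable per arm, and 51 / 0.8 = 63.75, so 64 enrolled. Route (b) changes the primary endpoint and needs an amendment.
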